1.7. MODIFICATIONS TO THE STATISTICAL SECTION OF THE PROTOCOL

The current SAP is based on Protocol v5.0. The following modifications were made to the statistical section of protocol.

Analysis Populations

- Additional analysis populations for efficacy endpoints and additional safety populations (Sections 3.1.1, 3.1.2, and 3.1.3) are defined to present data in a comprehensive manner.
- The definition of the modified intent-to-treatment (mITT) population is revised to include patients who did not meet all eligibility criteria but received Sponsor waiver to participate in the study. Waivers are not granted to patients who do not meet key eligibility criteria such as required prior therapies and measurable disease at baseline.
- The definition of the per-protocol population is revised (Section 3.1.1). The requirement of having completed at least one cycle of treatment is removed. Instead, patients are required to have at least one adequate post-baseline response assessment unless they died or withdrew from the study before that. Moreover, patients are required to have a compliance rate of at least 70% of selinexor instead of 80%.

Secondary Efficacy Endpoints

- The censoring rules for the secondary endpoints of duration of clinical benefits is revised to follow the TTP rule, such that it is consistent with the censoring rule for duration of response.
- The endpoint of duration of disease control is removed.

- The secondary endpoint of TTNT is added.

CCI [REDACTED]

- [REDACTED]
[REDACTED]
[REDACTED]

CCI [REDACTED]

- [REDACTED]
[REDACTED]
- [REDACTED]

1.8. STATISTICAL MODIFICATIONS MADE IN THE STATISTICAL ANALYSIS PLAN

Changes to Version 1.0

Section 1.2.3

- Clarified the definition of normal LDH at baseline (CCI [REDACTED]) to be “lower than or equal to upper limit normal”
- Clarified the hierarchical order of obtaining chromosomal abnormalities status: test results from central laboratories will be used if available, otherwise, test results from local laboratories will be used if available, otherwise, FISH results from initial diagnosis will be used if available.

Section 1.6

- The primary analysis will be performed after all patients have completed the Cycle 2 MM assessment, instead of Cycle 3 assessment
- Clarified the primary analysis will be performed based on a formal snapshot of database. In other words, data points in the database can still change after the primary analysis, but this snapshot will be frozen and will not change.

Section 2.6

- Revised the definition of visit windows for selected endpoints that are summarized/plotted by time points.

Section 2.7

- Added 2 subgroup factors on prior use of daratumumab

Section 3.1

- Added 2 additional analysis populations: the *All Penta-ref* population and the *Efficacy-Evaluable (EE) population*
- Removed the Part 1 six doses per cycle population and the Part 1 eight doses per cycle population

Section 3.1.2

- Corrected that the subset of safety population from Part 2 is different from the mITT population

Section 4.1.3

- CCI [REDACTED]
 - [REDACTED]
 - [REDACTED]
- CCI [REDACTED]
 - [REDACTED]

Section 4.2.1.3

- CCI [REDACTED]
 - [REDACTED]

Section 4.2.4-4.2.5

- Clarified that “missing 2 or more consecutively scheduled assessments” means a gap of 65 days or longer between 2 consecutive, adequate assessments.

Section 4.2.6.1

- Corrected the TTNT definition

Section 4.2.7.1

- Clarified for the calculation of overall survival, patients without on-study death events will be censored at the date of discontinuation from the study, or date of last participating visit (e.g., a telephone contact with patient status being alive), or database cut date, whichever is earlier.

Section 5.1.2.1

- Revised AE summary table

2. GENERAL STATISTICAL METHODS AND DATA HANDLING

2.1. GENERAL ANALYSIS METHODS

This is a single-arm, open-label study. All summary statistics will be computed and displayed among the corresponding analysis population, and by each scheduled assessment time point whenever applicable. Summary statistics for continuous variables will minimally include n, mean, standard deviation, minimum, median, and maximum. For categorical variables, frequencies and percentages will be presented. For time-to-event variables, the Kaplan-Meier method will be used for descriptive summaries. Graphical displays will be provided as appropriate. Data listings will be provided as appropriate.

2.2. MISSING DATA HANDLING IN DATA PRESENTATION

In general, missing baselines will not be imputed. The following approaches are default methods for missing data handling in summary tables.

- Categorical data at baseline will be summarized using counts (n) and percentages (%). Denominator will be the analysis population specified for the summary, unless otherwise specified. Missing data may be presented as a separate category.
- Continuous data: summaries will be based on observed data only.

2.2.1. Handling of Computation of Treatment Duration if Study Treatment End of Treatment Date is Missing

For the calculation of treatment duration, the date of the last dose of study treatment is equal to the date of last study treatment dosing reported on study treatment dosing form. If all the dosing dates are missing, then the duration is missing.

The last dose intake should be clearly identified on the eCRF dosing page and should not be approximated by the last returned package date.

2.2.2. Handling of Missing/partial Dates for Adverse Events or Concomitant Medications

In general, the imputation should be conservative such that onset dates should be imputed to be as early as possible and resolution dates will be imputed to be as late as possible. Impute resolution date first and then impute onset date using imputed resolution date. However, for categorization purpose, if the partial AE onset date information does not indicate whether the AE started prior to treatment or after the treatment-emergent adverse event (TEAE) period, the AE will be classified as treatment-emergent.

These data imputations are for categorization purpose or calculation of AE duration, and will not be used in listings. In data listings, an ongoing flag will be identified from the eCRF AE page.

Refer to the Karyopharm Biostatistics and Statistical Programming Rule Book for details on imputation methods.

2.2.3. Handling of Missing or Partial Birth Date for Calculation of Age

Refer to the Karyopharm Biostatistics and Statistical Programming Rule Book for details on imputation methods.

2.2.4. Handling of AEs When Date and Time of First Dose of Study Treatment Are Missing

When the date and time of the first dose of study treatment are missing, all AEs that occurred on or after signing the informed consent should be considered as TEAEs. The exposure duration should be kept as missing.

2.2.5. Handling of Missing Assessment of Relationship of AEs to Study Treatment

If the assessment of the relationship to study treatment is missing, then the relationship to study treatment in the frequency tables is considered as possibly related, but no imputation should be done at the data level or in data listings.

2.2.6. Handling of Missing Severity of AEs

If the severity is missing for one of the treatment-emergent occurrences of an AE, the maximal severity on the remaining occurrences will be considered. If the severity is missing for all the occurrences, a “missing” category will be added in the summary table.

2.3. STUDY TREATMENT DOSING DATE

Study treatment dosing date is the date on which a patient actually received study treatment (Sd, partial or complete).

The date of first study treatment is defined as the earliest date of non-zero dose of either selinexor or dexamethasone. The date of last study treatment is defined as the latest date of non-zero dose of either selinexor or dexamethasone.

2.4. STUDY DAY CALCULATION

Based on the study protocol, study Day 1 is the first study treatment dosing date. The day before Day 1 is considered Day -1; there is no Day 0.

A patient is considered as treated in a cycle if the patient received any non-zero dose of either selinexor or dexamethasone in that cycle.

Study day for a given assessment is defined as

- the assessment date – the date of first study treatment + 1 if the assessment date is on or after Day 1, or
- the assessment date – the date of first study treatment if the assessment date is before Day 1.

2.5. BASELINE MEASUREMENT

In general, the baseline value is defined as latest value prior to the first dose of study treatment. In the case an assessment performed on the same date as the first dose, but it is impossible to determine the evaluation time relative to the time of taking the first dose, the evaluation time will be assumed to be following the protocol-defined schedule.

Complete myeloma disease assessments are carried out during the Screening period and on Cycle 1 Day 1 (C1D1) prior to dosing Sd. In general, values on C1D1 are used as baseline. However, the IRC will determine which values are most clinically appropriate for use as

baseline, and if values are missing on C1D1, if the values obtained during the Screening period are appropriate as baseline.

2.6. VISIT WINDOWS

For safety data that are summarized/plotted by time points, non-missing assessments from all scheduled and unscheduled visits will be mapped to an appropriate analysis visit using a windowing scheme. Analysis visit windows are defined in Table 2-1. If there are 2 or more assessments mapped to the same analysis visit for a patient, the assessment that is closest to the target visit day will be used for analysis. If there are 2 or more assessments mapped to the same analysis visit with the same distance from the target visit day, then the latest one is selected for the analysis.

Table 2-1 Visit Windows for Clinical Laboratory Tests and Vital Signs

Analysis Visit Name	Target Visit Day	Study Day Range in Window
Baseline	Day 1	Prior to or on Day 1
Day 15	Day 15	Day 9 to 21
Day 29	Day 29	Day 23 to 35
Day 43	Day 43	Day 37 to 49
Day 57	Day 57	Day 51 to 63
Day 85	Day 85	Day 79 to 91
(every 28 days)		
...		
NOTE: Day 1 is the date of first study treatment dose. The visit window is +/- 6 days for post-baseline visits. Analysis visit and visit window may change for certain parameters depending on the data availability.		

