
Grade <math>\geq 3</math>                      Thrombocytopenia with bleeding
	
Delay/hold dosing until the bleeding has stopped and the patient is clinically stable. When resuming selinexor, see below:
 
For patients on 80 mg BIW (starting dose, Dose Level 0):                      Upon recovery to Grade <math>\leq 2</math> or baseline, dose reduce to 100 mg total dose per week (Dose Level -2) but dosed at the QW schedule until further recovery to Grade <math>\leq 1</math> and then may resume the total weekly dose scheduled as BIW (100 mg divided as 60 mg and 40 mg).
 
For patients on all other dose levels:                      Upon recovery to Grade <math>\leq 2</math> or baseline, dose reduce by one dose level, but dose the patient at the total weekly dose at the QW schedule until further recovery to Grade <math>\leq 1</math> or baseline and then may resume the total weekly dose scheduled as BIW.
 
For example, patients who were on dose level -2 (100 mg QW or divided as 60 mg and 40 mg) and need to de-escalate to dose level -3 (80 mg total per week), should be dosed at 80 mg QW until platelets recover to Grade <math>\leq 1</math> or baseline and then may resume the same total weekly dose of 80 mg total as a divided schedule of 40 mg BIW.

Toxicity and Intensity	Selinexor Dose Modification
	
**If the occurrence falls on Day 1 of a cycle, delay the start of the cycle and check platelet counts weekly until the bleeding has stopped, recovery to Grade <math>\leq 3</math> and the patient is clinically stable and follow the guidelines above.
 
CCI [REDACTED]

Neutropenia	
Grade 3 or 4 Neutropenia with fever (febrile neutropenia) or without fever	
Institute colony stimulating factors and prophylactic antibiotics as clinically indicated per institutional guidelines. Interrupt selinexor and check neutrophils weekly until recovery to Grade <math>\leq 2</math> or baseline and without fever (if febrile) and the patient is clinically stable. Reduce selinexor by 1 dose level when resuming.
 
If the occurrence falls on Day 1 of a cycle, delay start of a cycle and check neutrophils weekly until recovery to Grade <math>\leq 2</math> or baseline and without fever (if febrile) and the patient is clinically stable. Reduce selinexor by 1 dose level when resuming.

Anemia	

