##### Missed Doses

**If a dose was missed**, the schedule of that week should be altered to accommodate two doses in that week with at least 36 hours between two consecutive doses.

**If a dose must be skipped**, (e.g., due to recommendation of treating physician), the next dose will be taken as per schedule. Doses should not be administered less than 36 hours apart and all missed and delayed doses should be documented.

If a patient missed a full one or two-week period of dosing for non-study drug-related events (e.g., a required medical procedure or an unanticipated personal emergency), the days missed will be replaced. For example, if patient missed Cycle 2 Day 7 to Cycle 2 Day 14, then patient will start their next dosing on Cycle 2 Day 7 following the break. Similarly, if a patient misses Cycle 3 Day 1 to Cycle 3 Day 15, then the patient will start their next dosing on Cycle 3 Day 1. In this fashion, laboratory and radiographic assessments remain appropriate for timing of the administration of anti-cancer therapy.

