4.2.8. Quality of life (QoL)

4.2.8.1. Definition

Health-related QoL and potential for improvement over the course of the study will be assessed using the Functional Assessment of Cancer Therapy – Multiple Myeloma (FACT-MM) patient-reported outcome questionnaire that is specifically relevant to MM. This instrument combines the general version of the FACT (FACT-G) with a MM-specific subscale (14 items). The subscales for the FACT-G are Physical Well-Being (7 items), Social/Family Well-Being (7 items), Emotional Well-Being (6 items), and Functional Well-Being (7 items). The trial outcomes index (TOI; total of 41 items) will be the primary measurement of interest, comprised of the Physical and Functional subscales plus the MM-specific subscale. Each item is rated on a 5-point Likert scale, ranging from 0 (“Not at all”) to 4 (“Very much”), therefore the TOI has a score ranging from 0 to 120. The QoL assessment will be performed at Baseline (prior to first dose of study treatment), Day 1 of each cycle on or after the second, and at the Final visit.

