4.2.8.2. Analysis Methods

The primary analysis for QoL will be based on the change from baseline on the TOI score at each assessment time point, which will be summarized using descriptive statistics including mean, standard deviation, median, minimum, and maximum. The total score considering all 5 subscales as well as the 5 individual subscale sums of scores will be summarized similarly. The same analysis windows as in Table 2-1 will be used with the only exception that C1D15 is not considered as the questionnaire was not scheduled to administer during that visit.

The following supportive analyses will be conducted:

- In patients with a best response of confirmed PR or better
- In patients with a best response of confirmed MR or better

4.3.

CCI

CCI [REDACTED]
[REDACTED]

[REDACTED]
[REDACTED]
[REDACTED]

[REDACTED] [REDACTED]

[REDACTED]
[REDACTED]
[REDACTED]
[REDACTED]

- [REDACTED]
[REDACTED]
[REDACTED]

- [REDACTED]

- [REDACTED]

- [REDACTED]

[REDACTED]

- [REDACTED]

- [REDACTED]

[REDACTED]
[REDACTED]

[REDACTED]
[REDACTED]

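### The Table 2-1 visit windows leave gaps, so a cycle slip of one to three weeks leaves most or all later FACT-MM questionnaires without an analysis visit

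*SAP*

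**What the plan says.** SAP 2.6 introduces the windows with the words "For safety data that are summarized/plotted by time points" and undertakes that "non-missing assessments from all scheduled and unscheduled visits will be mapped to an appropriate analysis visit using a windowing scheme". Table 2-1 then gives a baseline row and targets at Days 15, 29, 43, 57 and 85, continuing every 28 days, with the note "The visit window is +/- 6 days for post-baseline visits". A second note allows visits and windows to be altered for some parameters according to what data exist, without saying how.

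SAP 4.2.8.2 extends the scheme to quality of life: "The same analysis windows as in Table 2-1 will be used with the only exception that C1D15 is not considered". The main analysis there is change from baseline in TOI at each time point. Questionnaires are due at baseline, "Day 1 of each cycle on or after the second", and at the final visit (SAP 4.2.8.1; the Schedule of Assessments shows EoT).

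SAP 2.4 counts study day from the first dosing date. The protocol, however, lets the cycle clock move:

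- Table 6, Grade 3 or 4 neutropenia found on Day 1 of a cycle: "delay start of a cycle and check neutrophils weekly until recovery". Similar instructions apply to Grade 4 thrombocytopenia, and to Grade 3 or higher with bleeding, found on Day 1.
- Section 11.1.5.4, a full week or two missed for reasons unrelated to study drug: "the days missed will be replaced".
- Section 11.1.5: a patient leaves treatment only when a drug-related delay exceeds 28 days.

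**The concern.** The undertaking and the table disagree. An assessment outside every window has no stated destination, so as written it drops out of the by-visit summary. The windows follow calendar time while visits follow the cycle clock. One slip therefore displaces every later Day 1 visit for that patient.

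The consequence is selective missingness by design: questionnaires that were completed leave the TOI summaries because the patient's cycle was delayed. FACT-MM is the exposed instrument, because no questionnaires are scheduled between cycles to fill an empty window. The EoT questionnaire has no row of its own. The note permitting windows to change leaves the repair until after the data can be seen.

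**Working it through.** **1. Reproduce the table.** Window = target +/- 6 days: 15 gives 9-21, 29 gives 23-35, 43 gives 37-49, 57 gives 51-63, 85 gives 79-91. All five printed ranges agree.

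**2. Find the gaps.** Days in no window are 2-8, 22, 36, 50, 64-78, 92-106, 120-134 and so on. Each gap after Day 63 holds 78 - 64 + 1 = 15 days. Each window holds 13, and 13 + 15 = 28, so 15/28 = 53.6% of days are uncovered. From Day 57 on, the gap is exactly target +7 to target +21.

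**3. Apply a slip.** Cycle k Day 1 falls on study day 1 + 28(k - 1) + s for a carried-forward slip of s days.

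| Slip | C3D1 | C4D1 | C5D1 |
|---|---|---|---|
| 0 | 57 (mapped) | 85 (mapped) | 113 (mapped) |
| 7 | 64 (none) | 92 (none) | 120 (none) |
| 14 | 71 (none) | 99 (none) | 127 (none) |
| 21 | 78 (none) | 106 (none) | 134 (none) |

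The protocol's own example, a patient who misses Cycle 3 Days 1 to 15 and restarts at Cycle 3 Day 1, corresponds to the 14-day row.

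**4. Add the allowed visit deviation.** The Schedule of Assessments permits +/-2 days. Take j = -2, -1, 0, 1, 2 with equal weight (an assumption). A Cycle 3 or later Day 1 visit is unmapped when 7 <= s + j <= 21.

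| Slip (days) | Offsets from target | Unmapped |
|---|---|---|
| 0 | -2 to 2 | 0/5 = 0% |
| 7 | 5 to 9 | 3/5 = 60% |
| 8 | 6 to 10 | 4/5 = 80% |
| 9-19 | all within 7 to 21 | 5/5 = 100% |
| 20 | 18 to 22 | 4/5 = 80% |
| 21 | 19 to 23 | 3/5 = 60% |

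On the slipped day itself, slips of 22-28 days land in the next target's window. They are relabelled, not lost.

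**5. Cycle 2 Day 1.** Its target is Day 29. A slip of 8-20 days gives Days 37-49, which is the Day 43 window. SAP 4.2.8.2 removes only the Cycle 1 Day 15 row for FACT-MM, so Day 43 remains although no questionnaire is due then. This visit is mostly moved, not lost. On the slipped day itself, slips of 7 and 21 days give Days 36 and 50, both in gaps.

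**6. EoT.** If an EoT visit were equally likely on any day after Day 63 (an assumption), it would be unmapped 15/28 = 54% of the time.

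**7. Patients without a slip.** No Day 1 visit is lost if +/-2 days is counted from the nominal day. If deviations accumulate from visit to visit, with uniform steps, a Cycle 5 visit needs four steps summing to +/-7 or +/-8. That has probability 2 x (4 + 1)/625 = 1.6%, rising to about 8% at Cycle 8. Cycle 1 Day 8 safety visits (Days 7-9) are unmapped on Days 7 and 8 for everyone.

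**8. Illustration of scale only.** Assume a per-cycle delay probability of 5%, 10% or 15%, with slips of one, two or three weeks split 70/20/10. Simulation then leaves 12.8%, 22.7% or 31.1% of Cycle 3-7 Day 1 questionnaires unmapped. None of these inputs is in the documents.

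**The case against.** The strongest reply is that the SAP nowhere says out-of-window values are discarded. It says the opposite in general terms, allows windows to change, and promises QoL summaries at each assessment time point. That is fair as a reading of intent, but it supplies no rule. A programmer following Table 2-1 has nowhere to put a Day 71 questionnaire.

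A second reply limits the route, and it stands. The toxicity-driven delay of a cycle start is stated only for certain cytopenias found on Day 1. Grade 3 thrombocytopenia without bleeding does not call for a hold at first occurrence, and doses missed for infection are not replaced. Replacement of missed weeks covers only reasons unrelated to study drug. A reader might infer that all the loss is driven by toxicity. The documents support only that it falls on patients whose cycles slipped, for either kind of reason. Also, Protocol 9.9.2 asks for FACT-MM before other procedures, so the first affected questionnaire may already be complete on the planned day. Later ones are still displaced.

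Third, a reader might infer that later visits will look better than they were. That requires delayed patients to score worse. A delayed Day 1 follows recovery and time off drug, so neither the sign nor the size is established.

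Fourth, a reader might extend the point to the safety conclusions. The specified laboratory and vital-sign outputs are worst-grade, shift and threshold tables (SAP 5.3.2 and 5.4), and box plots over time are optional. Protocol 13.3.7.2 and 13.3.7.3 do call for summaries at each evaluation, but weekly counts during a delay can fill windows.

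**Conclusion.** The defect is real and follows from the table alone: the windows do not cover what SAP 2.6 says they cover. Its main effect is on FACT-MM. A carried-forward slip of 7-21 days leaves 60% to 100% of Cycle 3 and later Day 1 questionnaires unmapped, against 0% of Day 1 visits without a slip. These percentages assume that questionnaires are taken at the actual start of each cycle, that deviations are spread equally over +/-2 days from the nominal day, and that unmapped values are left out. EoT questionnaires after Day 63 can also be lost.

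The loss is selective, but its frequency and the size and direction of any TOI bias cannot be set from the documents. It would also be wrong to say that undelayed patients lose nothing: that holds only for Day 1 visits, since EoT visits and Cycle 1 Day 8 safety values can fall in gaps for anyone. ORR does not use these windows, and the effect on safety reporting is minor. This should be corrected, but it does not threaten the primary conclusion.

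**What to change.** - **FACT-MM:** map by nominal cycle and day. Alternatively, use contiguous nearest-target windows with targets only where a questionnaire is due (Days 29, 57, 85, then every 28 days), with no Day 15 or Day 43 visit and a stated rule for ties. With ties to the earlier target, windows from Day 57 on run from target -13 to target +14. Nothing after baseline is then lost, but slips beyond 14 days are labelled one visit late. Nominal mapping avoids that and is preferable.
- **Safety data:** make the windows contiguous, for example Day 8 = 2-11 where data are collected, Day 15 = 12-22, Day 29 = 23-36, Day 43 = 37-50, Day 57 = 51-71, Day 85 = 72-99, then target -13 to +14.
- **EoT:** add a separate analysis visit for both.
- **Timing:** write the rule into the SAP before the primary-analysis snapshot, in place of the note that windows may change.

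The cost is SAP wording, a small programming change and, where windows are used, a wider spread of timing within each visit (up to 28 days instead of 13). No new data are needed.

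### The ±6-day analysis windows in SAP Table 2-1 leave gaps, although SAP 2.6 says all visits will be mapped, and the FACT-MM windows keep a Day 43 target with no scheduled questionnaire (minor)

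*SAP*

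**What the plan says.** SAP 2.6 covers safety data summarised or plotted by time point. It says that "non-missing assessments from all scheduled and unscheduled visits will be mapped to an appropriate analysis visit using a windowing scheme". Table 2-1 then lists a baseline row (up to and including Day 1) and post-baseline targets at Days 15, 29, 43, 57 and 85, continuing every 28 days. Its note fixes the width: "The visit window is +/- 6 days for post-baseline visits". The same note adds that "Analysis visit and visit window may change for certain parameters depending on the data availability", without saying which parameters or by what rule. Where several values fall in one window, the one nearest the target is used, and the later one if distances tie.

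The time scale is calendar days. Under SAP 2.4, "study Day 1 is the first study treatment dosing date", and nothing resets the count when a cycle starts late.

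SAP 4.2.8.2 makes the change from baseline in the FACT-MM trial outcome index, at each assessment time point, the primary quality-of-life analysis. It reuses Table 2-1 "with the only exception that C1D15 is not considered as the questionnaire was not scheduled to administer during that visit".

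The protocol provides for cycles to move. Section 11.1.5 tolerates drug-related delays of up to 28 days. Table 6 postpones a cycle when certain thrombocytopenia or neutropenia events fall on its Day 1, with weekly counts meanwhile. Under Missed Doses (11.1.5.4), after a full one- or two-week break for reasons unrelated to study drug, "the days missed will be replaced".

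**The concern.** Thirteen-day windows around targets 14 days apart, and later 28 days apart, cannot cover every study day. The mapping sentence and the table beneath it therefore disagree, and a programmer following the table will drop values that the text says are kept. SAP 2.2 bases continuous summaries on observed data only, so a patient whose values fall in a gap simply leaves that row.

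What is at stake is whether by-visit rows represent the patients still being assessed. Some cycle shifts follow haematological toxicity. If patients with such shifts leave the later rows, those rows describe mainly patients whose cycles stayed near schedule, and a single-arm study has no control arm against which to notice this.

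The FACT-MM problem is separate. The SAP's reason for removing C1D15, that no questionnaire was scheduled then, applies equally to C2D15.

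**Working it through.** **Reproducing Table 2-1.** Window = target ± 6:
- 15 → 9-21
- 29 → 23-35
- 43 → 37-49
- 57 → 51-63
- 85 → 79-91

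All five match the printed ranges. Continuing every 28 days gives 107-119, 135-147 and so on.

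**Days in no window.** Baseline ends on Day 1, so the gaps are Days 2-8 (7 days), 22, 36 and 50 (1 day each), then 64-78, 92-106, 120-134 and so on (15 days each).
- Days 2-63: 7 + 1 + 1 + 1 = 10 of 62 days.
- Each later 28-day interval: 28 − 13 = 15 days, and 15/28 = 54%.
- Days 2-365: 175 of 364 days (48%).

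**Visits on schedule.** Visit tolerances are from protocol Table 1 and SAP Table 7-1.

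| Visit | Study days | Analysis visit |
|---|---|---|
| C1D8 (±1) | 7, 8 | none |
| C1D8 (±1) | 9 | Day 15 |
| C1D15 (±1) | 14-16 | Day 15 |
| C2D1 (±2) | 27-31 | Day 29 |
| C2D15 (±2) | 41-45 | Day 43 |
| C3D1 (±2) | 55-59 | Day 57 |
| C4D1 (±2) | 83-87 | Day 85 |

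Only C1D8 fails without any delay. Both schedules place limited chemistry and vital signs at that visit.

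**Visits after a cumulative shift of s days** (new day = nominal day + s, taken at the target day):

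| s | C2D1 (29) | C2D15 (43) | C3D1 (57) | C4D1 (85) | C5D1 (113) |
|---|---|---|---|---|---|
| 0-6 | Day 29 | Day 43 | Day 57 | Day 85 | Day 113 |
| 7 | none | none | none | none | none |
| 8-20 | Day 43 | Day 57 | none | none | none |
| 21 | none | none | none | none | none |
| 22-28 | Day 57 | none | Day 85 | Day 113 | Day 141 |

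Example: s = 14 moves C3D1, C4D1 and C5D1 from Days 57, 85 and 113 to Days 71, 99 and 127, all in gaps. From C3D1 on, a shift of 7 to 21 days loses the Day 1 visit, and 22 to 28 days places it one visit late.

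**FACT-MM.** Both schedules list the questionnaire at screening, Day 1 of Cycle 2 and later cycles, and end of treatment. Neither lists it at C1D15 or C2D15. With only Day 15 removed, the Day 43 row (Days 37-49) remains, and no form is planned for it. It can fill only with forms that land there by accident of timing: a C2D1 form delayed by 8 to 20 days (29 + 8 = 37; 29 + 20 = 49), an end-of-treatment form in that interval, or an unscheduled one.

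**The case against.** The strongest reply is that little depends on these windows. ORR and the time-to-event endpoints do not use them. Neither do the AE tables, worst-grade summaries, shift tables (baseline to worst and to last) or threshold tables, so a toxic value on Day 5 or Day 70 still reaches the analyses built to detect it. The over-time laboratory display named in SAP 5.3.2 is a set of optional box plots, and FACT-MM is summarised descriptively. All of that stands and is why the point is minor. Some output is still touched: protocol 13.3.7.2 and 13.3.7.3 call for laboratory and vital-sign summaries at each on-study evaluation, and the primary quality-of-life summary is by time point.

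A second reply is that narrow windows are a legitimate choice that keeps displayed values near their nominal day, and that the mapping sentence may only mean unscheduled values are eligible. If so, the sentence should say that values outside the windows are not displayed. The note allowing windows to change does not settle it, because it gives no rule and leaves the choice until data are available.

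A reader might go further and infer that delayed patients in general disappear, that these are the least tolerant patients, and that the rows therefore look too favourable. The documents do not support this. Shifts under 7 days map correctly, and shifts of 22 to 28 days map one visit late. The missed-weeks rule concerns breaks unrelated to study drug; the toxicity delays come from Section 11.1.5 and Table 6. Those haematological delays bring weekly counts, and unscheduled counts inside a window can still fill a row.

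**Conclusion.** The inconsistency in SAP 2.6 is real and follows from the printed ranges alone. So does the FACT-MM oversight, by the SAP's own reason for dropping C1D15. Severity is minor.

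The figure of 15 in 28 should not be read as a loss of 54% of assessments or patients. It is a share of calendar days after Day 63, and on-time visits from C1D15 on all map. Loss depends on how many patients carry a cumulative shift of 7 to 21 days at a given visit, which the documents do not report. Loss of patients with toxicity delays could make later rows unrepresentative, but neither the size nor the direction can be computed.

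The shift results assume that the delay persists, that assessments move with the cycle, that visits occur at the shifted target day, and that Table 2-1 is applied as printed. A visit tolerance of ±2 days blurs the boundaries by that amount.

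**What to change.** 1. Make the Table 2-1 windows contiguous, split at midpoints between targets, and keep the nearest-to-target rule. With midpoint days given to the earlier visit, the existing targets yield Days 2-22, 23-36, 37-50, 51-71, 72-99, 100-127 and so on, with no unmapped day.
2. Add a Day 8 target for parameters scheduled at C1D8. The midpoint of 8 and 15 is 11.5, so the first window becomes Days 2-11 for Day 8 and Days 12-22 for Day 15.
3. For FACT-MM, drop both Day 15 and Day 43 as targets, or analyse by nominal cycle visit. If windows are kept, the midpoint of 29 and 57 is Day 43, giving Days 44-71 for Day 57, and the start of the Day 29 window must be stated.
4. Replace the open note on changing windows with the specific exceptions, fixed before the analysis.

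The cost is an edit to one SAP table and two paragraphs, with no change to data collection or conduct. The downside is that some displayed values lie further from target, up to about 14 days (Day 71 against Day 57; Day 99 against Day 85). A visit shifted by more than 14 days would still carry the next visit's label unless nominal cycle visits are used.
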